7.8 General Concomitant Medication and Supportive Care Guidelines

- 1) Transfusions:
 - a) Packed red blood cell (PRBC) transfusions for HGB <7g/dL, or symptomatic anemia, are permitted.
 - b) Platelet transfusions are permitted for bleeding or platelet counts < 10,000/ μ L.
- 2) Growth Factors and Antimicrobials:
 - a) Administration of ESAs is not be permitted on the trial1.
 - b) Administration of GCSF and use of prophylactic antimicrobials for severe neutropenia is permitted at the discretion of the investigator.

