Study Description:	
This is a two-tiered single arm Phase 2 trial of vactosertib (TEW-7197) for the treatment of anemia in Ph-neg MPNs. Both tiers use a rule-based, accelerated dose escalation scheme to efficiently assess the potential of vactosertib to safely and effectively treat anemic patients with Ph-neg MPNs. The first tier of this trial (Tier 1) is an intra-patient dose finding study in 12 patients that uses a low starting dose of vactosertib for all patients. Treatment dose is escalated according to prospectively-defined rules, and a toxicity and treatment effect algorithm (Table 3 in section 7) during the period of 16 weeks (4 treatment cycles). If pre-established efficacy and safety endpoints are met (section 12.1), then Tier 1 of the study will be followed by a Tier 2 expansion study with an additional 25 patients for a period of 24 weeks (6 treatment cycles).
 
Vactosertib will be administered in combination with stable dose of current therapy. Prior to enrollment patients must be on a stable dose of their current therapy for 3 months prior to entering the study. For patients not receiving cytoreductive therapies (e.g., interferon, hydroxyurea, DNA hypomethylating agents or other cytotoxic chemotherapy) must be off their most recent for a period of at least 14 days or 5 half-lives, whichever is longer. Supportive care measures including packed red blood cell (PRBC) transfusions for HGB <7g/dL, or symptomatic anemia, will be permitted. Administration of erythropoiesis stimulating agents (ESAs), however, will not be permitted on the trial (patients recruited would have serum EPO >125 U/L above which the benefit of ESAs is not supported)¹.

Sample Size:	Total = 37 subjects (N = 12 for Tier 1, N = 25 for Tier 2)
Enrollment:	This study will enroll 37 subjects and screen up to 100 subjects.
Study Population:	Patients of age \geq 18 with anemia due to Ph-neg MPNs
Enrollment Period:	72 months

Study Design:

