4.2 Inclusion Criteria

- Age ≥ 18 years
- Patients meet the WHO 2016 criteria for a Ph-neg MPN (including PV, ET, MF, MDS/MPN, MPN-U).
- Patients with MF must have DIPSS+ Intermediate or High-risk MF (primary or post-PV/ET)
- Patients should be on a stable dose of current cytoreductive therapy for at least 3 months prior to C1D1.
- Anemia as defined by HGB < 10 g/dL, or transfusion of ≥ 2 packed red blood cell (PRBC) unit within the past 4 weeks with HGB ≤ 8.5g/dL. The anemia, in the investigator's opinion,

must be due to underlying MPN and not due to other causes such as the toxic effects of prior cytoreductive chemotherapy.

- Ineligible, unsuitable or refractoriness to ESA therapy defined as any of the following:
 - Serum erythropoietin (EPO) >125 U/L⁴.
 - Proven ESA unsuitability is defined by history of any of the following:
 - Loss of erythroid hematologic improvement while receiving stable or increased ESA dose; or
 - ESA-attributed toxicity that, in the treating physician's opinion, makes ESA therapy unsuitable for subject.
 - ESA refractoriness defined by lack of erythroid hematologic improvement to ESA:²⁷
 - Less than 1.5 g/dL increase in hemoglobin after at least 6 weeks of ESA therapy; or
 - Ongoing transfusion dependence that has not been reduced by >4 U over an 8-week period compared to ESA pre-treatment 8 weeks.
- ECOG Performance status ≤ 2
- Able to swallow tablets
- Able to give written informed consent
- Willing and able to comply with scheduled visits, treatment plans, tests and procedures.
- Acceptable Organ Function as defined by:
 - serum creatinine ≤ 2 mg/dL or > 50 mL/min/1.73m² by direct measure
 - AST(SGOT)/ALT(SGPT) ≤ 3 x institutional upper limit of normal
 - Total bilirubin ≤ 2 x institutional upper limit of normal

Note: Subjects with documented diagnosis of Gilbert's Syndrome resulting in elevated total bilirubin levels will be eligible provided all other eligibility criteria are met.

Note: Subjects with total bilirubin 2-3 mg/dL and direct (conjugated) bilirubin in the normal range will be eligible, provided all other eligibility criteria are met.

- Acceptable Cardiovascular status as defined by:
 - Mean QT interval corrected for heart rate using Fridericia's formula (QTcF) ≤ 450 ms for males, and ≤ 470 ms for females on screening ECG.

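### No rule keeps ESA dosing out of the baseline windows, so a patient who stops a partly effective ESA around entry has the lost ESA effect counted against vactosertib

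*Combined protocol and SAP*

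**What the plan says.** ESAs are prohibited during the study (section 7.8: "Administration of ESAs is not be permitted on the trial"). The Study Description in section 1 gives the reason: "patients recruited would have serum EPO >125 U/L above which the benefit of ESAs is not supported".

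Section 4.2 does not make that EPO level a requirement. Its criterion reads "Ineligible, unsuitable or refractoriness to ESA therapy defined as any of the following", and a serum EPO above 125 U/L is one alternative among several. The others are:

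- lost response: "Loss of erythroid hematologic improvement while receiving stable or increased ESA dose";
- ESA toxicity that, in the physician's opinion, "makes ESA therapy unsuitable for subject";
- refractoriness by hemoglobin: "Less than 1.5 g/dL increase in hemoglobin after at least 6 weeks of ESA therapy";
- refractoriness by transfusion: "Ongoing transfusion dependence that has not been reduced by >4 U over an 8-week period", compared with the 8 weeks before ESA treatment.

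Baseline hemoglobin is the median over the 28 days before Cycle 1 Day 1 (section 6.1 footnote g, section 6.3.1.4, Table 3 footnote). Transfusion history covers the 8 weeks before screening (section 6.1 footnote h, section 6.2.2.10). Section 10.1.3 counts an erythropoietic response if hemoglobin rises 1.5 g/dL from baseline, if the transfusion rate falls to half or less, or if transfusions fall by at least 4 units over 8 weeks. It is a Tier 2 primary endpoint and one of three ways to meet the Criteria for Clinical Benefit.

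**The concern.** This is a single-arm before/after comparison in anemia. If the before period includes an ESA that is doing something and the after period forbids it, the difference mixes vactosertib's effect with ESA withdrawal, and no control arm separates them. The reason given for dismissing ESA effect, a high EPO level, does not cover everyone whom section 4.2 admits.

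Two things are at stake. A true erythropoietic responder may be missed, in the Tier 2 primary endpoint and in the composite go/no-go counts. And because Table 3 uses the same baseline, a patient may be moved to a higher dose in response to a baseline artefact.

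**Working it through.** **Step 1. Which entry routes leave ESA effect to lose (section 4.2)?**

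| Route | Effect left to lose |
|---|---|
| EPO above 125 U/L | Little, on the plan's own rationale |
| Lost response on ESA | Little |
| ESA toxicity | No cap on prior benefit |
| Refractory, hemoglobin | Up to just under 1.5 g/dL |
| Refractory, transfusion | Up to 4 units per 8 weeks |

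The last two are upper bounds, not typical effects.

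**Step 2. Does any text close the gap?** Neither 4.2 nor 4.3 sets an ESA-free interval. Two sentences in the Study Description come close.

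- The washout of 14 days or 5 half-lives lacks its noun, is framed around cytoreductive therapy and does not name ESAs. Even if it applied, an ESA stopped 14 days before Cycle 1 Day 1 leaves 14/28 = half of the hemoglobin window on drug.
- Patients "must be on a stable dose of their current therapy for 3 months prior to entering the study". Section 4.2 limits this to cytoreductive therapy. Read to include an ESA, it would keep the patient on ESA through baseline and off it on study.

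**Step 3. Per-patient size.** If L g/dL of ESA effect is lost after baseline, the measured change is the true gain minus L, so a measured +1.5 needs a true gain of 1.5 + L: 2.0 for L = 0.5, 2.5 for L = 1.0, and nearly 3.0 at the refractoriness limit. Likewise, losing a saving of 4 units per 8 weeks cancels a true reduction of 4 units.

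Example (assumed values: baseline 8.5 on ESA, L = 1.0, true gain 2.2, no transfusion):

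- On-study hemoglobin is 8.5 − 1.0 + 2.2 = 9.7.
- Against the on-ESA baseline the change is 9.7 − 8.5 = +1.2: a non-responder. Table 3 says Escalate (at most 10, and gain at most 2, with the toxicity conditions met).
- Against an ESA-free baseline of 7.5 the change is 9.7 − 7.5 = +2.2: a responder. Table 3 says Maintain (gain above 2).

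The values were chosen to cross both thresholds. They show the mechanism, not its frequency.

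**Step 4. Trial level.** Inputs from Table 4: at least 1 responder of 12, then at least 4 of 37 in total, with response rates 0.05 and 0.20.

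Pass(p) = Σ over x = 1 to 12 of P[Bin(12, p) = x] × P[Bin(25, p) ≥ 4 − x]

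This reproduces the plan: 9.35% at p = 0.05 and 90.2% at p = 0.20, both inside the stated 10% error limits.

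With masking, p = 0.20 × (1 − h·s·m). Here h is the share of responders who qualify only by erythropoiesis, s the share of patients affected, and m the fraction of those responses masked. The documents give none of the three, so all are assumed. With h = 0.50:

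| s | p at m = 1 | Power, m = 1 | Power, m = 0.5 |
|---|---|---|---|
| 2% | 0.198 | 89.9% | 90.0% |
| 5% | 0.195 | 89.3% | 89.8% |
| 10% | 0.190 | 88.2% | 89.3% |
| 20% | 0.180 | 85.7% | 88.2% |
| 30% | 0.170 | 82.7% | 87.0% |

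Varying h with m = 1: at s = 10%, h = 0.25 gives 89.3% and h = 0.75 gives 87.0%. At s = 30% they give 87.0% and 77.3%.

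Under the null with h = 0.50, s = 10%, m = 1: p = 0.05 × 0.95 = 0.0475 and the pass rate is 8.1%, below the unmasked 9.35%.

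**The case against.** The strongest reply is that the bias needs several conditions at once. The patient must enter by toxicity or refractoriness, still be on an ESA near entry, be gaining from it, stop in or just after the windows, and respond only by erythropoiesis. The toxicity route rests on a history that already makes ESA therapy unsuitable. The refractory route is headed as lack of improvement, and a gain near 1.5 g/dL is its edge. Section 2.3 says that ESAs are often ineffective in this population. All of this stands, and it is why the affected share is probably small.

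The existing text may also cover part of the gap. If the ban runs from consent, it overlaps much of the 28-day screening period. If three stable months on current therapy is read broadly, a patient who stopped an ESA weeks before entry would not qualify. Neither reading is explicit, section 4.2 is narrower than the synopsis, and a ban from consent does not deal with carry-over. Both readings reduce the problem without settling it.

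Finally, a dose-free window is not an effect-free window: section 4.2 itself allows at least 6 weeks to judge an ESA's effect on hemoglobin. Two of the three erythropoietic criteria are transfusion-based, and the 8-week look-back would still overlap ESA use in some patients. That also stands and limits what the fix can promise.

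**Conclusion.** The gap is real. Following the plan as written can set an on-ESA baseline against off-ESA values in an endpoint that also drives dosing. Its expected size is small: about 0.4 to 2 points of composite power if 2% to 10% of patients are affected, given that half of responders qualify only by erythropoiesis and all affected responses are masked. Confidence is medium, because no document gives the share of patients entering on an ESA.

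Three stronger readings are not supported.

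- A reader might infer a risk of a false positive result. The direction is the opposite: a contaminated baseline makes response harder to show.
- A reader might infer that the go/no-go decision is seriously weakened. The 77.3% figure needs 30% affected, 75% erythropoiesis-only and complete masking together, and nothing in the documents points there. Symptom and spleen responses are not directly affected.
- A reader might infer that everyone entering without a high EPO level is affected. Those who have lost their ESA response have little left to lose, and those who stopped well before the windows add no bias.

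This is a low-cost improvement to consider, not a defect in the design's error rates.

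**What to change.** In sections 4.2 and 6.3.1.4, require that the last ESA dose precede the 28-day baseline hemoglobin window. Because section 6.2 has treatment start within 28 days of screening, this means stopping the ESA no later than the start of the D-28 screening period. Record the date of the last ESA dose with the medications already collected at screening. Repeat the erythropoietic and composite response counts without patients whose 8-week transfusion look-back overlaps ESA use. State that the rule reduces ESA carry-over but may not fully remove it.

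The cost is one eligibility line, one baseline line, one recorded date and one sensitivity count, plus a start delayed by up to about 4 weeks for the few patients coming off an ESA, who must stop it anyway. Requiring the full look-back to be ESA-free as well could mean up to about 12 weeks off ESA (8 weeks before screening plus 4 of screening). That is too long to ask of anemic patients, so flagging and a sensitivity count are preferable there.

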7.9 Duration of Therapy and Criteria for Removal from Study

- 7.9.1. Tier 1 duration is 16 weeks (4 treatment cycles) and Tier 2 duration is 24 weeks (6 treatment cycles).
- 7.9.2. In the absence of treatment delays due to adverse event(s), treatment may continue for 6-10 cycles or until one of the following criteria applies:
 - 7.9.2.1. Disease progression at the MTD,
 - 7.9.2.2. Intercurrent illness that prevents further administration of treatment,
 - 7.9.2.3. Unacceptable adverse events, specifically:
 - Adverse event(s) that necessitate a dose hold for >28 days,
 - Adverse events that occur at DLO
 - 7.9.2.4. Patient decides to withdraw from the study, or
 - 7.9.2.5. General or specific changes in the patient's condition render the patient unacceptable for further treatment in the judgment of the investigator.

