6.3.2.3. Dose Adjustment Testing and Procedures (*section 6.3.2.2*)

6.3.2.4. If Day 1 of Cycle,

- Pill Counts to assess compliance (subjects return all vials at visit for pill counts).
- Dispense study drug (vactosertib 50 mg tabs) for one cycle from research pharmacy and deliver to subject during clinic visit.
- Research blood sample (20mL) will be collected one hour after vactosertib dose (also collected on C1D8).

6.3.3. **Dose Adjustment Decision** ([see Table 3 section 7](#))

6.3.3.1. **Escalate** to next dose level

- Subject will receive one dose of vactosertib at escalated dose level under supervision of treating physician or research study nurse.
- Research blood sample (20mL) will be collected approximately 1hr after escalated dose taken.
- If dose is at maximum level (DL4), and patient has at least stable disease, then patient can remain on study at maximum level (DL4).
- If dose is at maximum level (DL4), and patient has progressive disease, then patient will be removed from study.
- Subject will return for Follow-up Testing and Procedures in 7 (\pm 2) days from start of new dose level.

6.3.3.2. **Maintain** current dose level

6.3.3.2.1. **New Maintain Decision:**

- Subject will return for Follow-up Testing and Procedures in 14 (\pm 3) days.

6.3.3.2.2. **Ongoing Maintain Decision:**

- After at least two, consecutive Maintain dose-adjustment decision at the same dose level, subject will return for Follow-up Testing and Procedures no later than Day 1 of the next cycle of vactosertib.

6.3.3.3. **Hold** vactosertib

- If last dose received is at minimum dose level (DL0), patient will be removed from study. Otherwise:

6.3.3.3.1. **New Hold Decision**

- Subject will return for Follow-up Testing and Procedures in 7 (\pm 2) days.

6.3.3.3.2. **Ongoing Hold Decision**

- If dose is held > 28 days, subject will be removed from study.
- If dose is held < 28 days, subject will return for Follow-up Testing and Procedures in 7 (\pm 2) days

6.3.3.4. **Restart** vactosertib

- Vactosertib dose will be reduced to one dose level lower than the last dose level received.
- If last dose received was at minimum dose level (DL0), patient should have already been removed from study.
- Subject will return for Follow-up Testing and Procedures in 7 (\pm 2) days from start of new dose level.
- Subject will receive one dose of vactosertib at restarted dose level under supervision of treating physician or research study nurse.

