7.7.2 Dosing Delays/Dose Modifications for vactosertib

Clinical Parameter	Escalate to Next Dose Level	Maintain Current Dose Level	Hold Dose	Restart After Dose Hold
Erythropoietic Response	Inadequate	Adequate		
Hemoglobin (HGB) absolute value, change in HGB from baseline*, and Erythrocyte transfusion	HGB ≤10 g/dL AND ≤2 g/dL increase from baseline HGB OR any Erythrocyte transfusion	HGB >10 g/dL OR >2g/dL increase from baseline HGB AND No Erythrocyte transfusion	HGB >12 g/dL	HGB<12 g/dL
Current Toxicity (CTCAE v5)	≤Grade 2	≤Grade 2 OR >Grade 2 not requiring change in treatment	>Grade 2 Requiring Change in Treatment	<Grade 2 and Requiring No New Change in Treatment
Dose hold Toxicity during Cycle	Dose Hold Not Required During Cycle	Dose Hold Not Required During Cycle		
Current Dose Dose Levels: (DL0) 50 mg daily; (DL1) 50 mg bid; (DL2) 100 mg bid; (DL3) 150 mg bid; (DL4) 200 mg bid.	< Highest Dose Level	≤ Highest Dose Level		Most Recent Dose >(DL0)
Dosing schedule, 5 days on, 2 days off				
Rule	All True	All True	Any True	All True
Next Study Visit [†]	7±2 days	1 st Maintain [§] 14±3 days 2 nd or greater Maintain D1 of next cycle	7±2 days	7±2 days

Table 3: Intrapatient Dose Adjustment Rules.

The parameters shown are used to adjust the vactosertib dose on a continuing basis. The dose is escalated to the next level if ALL criteria for escalation are met. The decision to Hold vactosertib is made if ANY hold criteria is met at any point during the cycle. Otherwise the dose level is maintained. The criteria to Escalate, Maintain or Hold a dose are non-overlapping. Dose decrements by one level will follow any HOLD. * Baseline HGB is defined as the median HGB in the 4 weeks prior to D1 of protocol treatment. † Subject will maintain a diary of adverse events between study visits. [§]Visits are weekly if there is a dose change (Escalate, Hold or Restart). Visits are bi-weekly if the decision is to Maintain the current dose. Visits are extended to every 4 weeks (D1 of each new cycle) after the second or greater, consecutive Maintain decision.

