13.1 Adverse Event Definition

An adverse event (also referred to as an adverse experience) can be any unfavorable and unintended sign (e.g., an abnormal laboratory finding), symptom, or disease temporally associated with the use of a drug, and does not imply any judgment about causality. An adverse event can arise with any use of the drug (e.g., off-label use, use in combination with another drug) and with any route of administration, formulation, or dose, including an overdose.

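### The removal rule for adverse events at DL0 (7.9.2.3) has no severity threshold and conflicts with 6.3.3.3 and Table 3

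*Combined protocol and SAP*

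**What the plan says.** Section 7.9.2.3 introduces its list with "Unacceptable adverse events, specifically" and gives two bullets. The first is limited to events that need a dose hold of more than 28 days. The second is "Adverse events that occur at DLO", where the last character is the document's spelling of DL0. It states no grade, attribution or hold condition. Section 13.1 says an adverse event "can be any unfavorable and unintended sign (e.g., an abnormal laboratory finding), symptom, or disease temporally associated with the use of a drug". Section 8 refers to 7.9 for discontinuation, and Section 15 names it as the place where stopping rules for individual patients are found.

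The dose-adjustment rules differ. Section 6.3.3.3, under the Hold decision, states: "If last dose received is at minimum dose level (DL0), patient will be removed from study". In Table 3 (7.7.2) the toxicity trigger for Hold is ">Grade 2 Requiring Change in Treatment". If no Hold criterion is met, the patient is maintained or escalated. Table 3 also holds for hemoglobin above 12 g/dL, and its caption adds "Dose decrements by one level will follow any HOLD". Section 6.3.3.4 says the same of a restart: "Vactosertib dose will be reduced to one dose level lower than the last dose level received".

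**The concern.** For an adverse event at DL0 the protocol contains two removal rules with different thresholds, and the sections on discontinuation and safety monitoring point staff to the one without a threshold. Applied as written, 7.9.2.3 would take off treatment a patient whom Table 3 keeps on, or has just restarted.

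A patient without a dose-limiting toxicity (DLT) could then leave before completing the 8 weeks of benefit in Table 5, or before the four cycles that 12.6.2 requires for response assessment. The decision cut-offs in Table 4 are small: at least 1 responder to open Tier 2 and at least 4 at the end. One lost responder would matter if the count stood at a cut-off.

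**Working it through.** The plan gives no figure to reproduce on this point. The check compares the rules and then works out from the visit schedule how long a patient is exposed to the conflict.

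**1. The two rules applied to a patient at DL0**

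| Adverse event at DL0 | 7.9.2.3, read literally | 6.3.3.3 with Table 3 |
|---|---|---|
| Grade 1 or 2 | Remove | Maintain or escalate |
| Above Grade 2, no treatment change needed | Remove | Maintain |
| Above Grade 2, treatment change needed | Remove | Hold, therefore remove |

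The rules agree only in the last row. In the middle row a non-hematologic event will usually be a DLT under 13.1.1, so the effect on the responder count lies mainly in the first row.

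**2. Who can be at DL0 without a DLT**

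- *Step-down from DL1.* Tier 1 starts at DL1 (50 mg twice daily). A hold for hemoglobin above 12 g/dL, or a toxicity hold that is not a DLT, leads to restart at DL0. Table 3 then keeps the patient there while hemoglobin is above 10 and not above 12 g/dL, no red cells are transfused, and toxicity is Grade 2 or lower.
- *Tier 2 start at DL0.* This applies only if 6.3.6.3 selects DL0. Exposure is then about one week (7 ± 2 days) for patients who escalate at the first visit.

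**3. Whether the hemoglobin step-down patient is already a responder**

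- Section 10.1.3 requires a rise of 1.5 g/dL from baseline, and 12 − 1.5 = 10.5. Hemoglobin above 12 g/dL therefore meets the criterion for any baseline median up to 10.5 g/dL.
- Section 4.2 requires "Anemia as defined by HGB < 10 g/dL", or 8.5 g/dL or lower with transfusion. From a baseline below 10 the rise exceeds 12 − 10 = 2 g/dL.

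**4. Days at DL0 within the 8-week period of Table 5 (56 days)**

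Assume benefit is first recorded at the visit that triggers the hold. Days at DL0 = 56 − length of hold:

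- 7-day hold: 56 − 7 = 49
- 5-day hold: 56 − 5 = 51
- 9-day hold: 56 − 9 = 47
- 28-day hold, the longest permitted: 56 − 28 = 28

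If benefit was recorded *d* days before the hold visit, each figure falls by *d*. With *d* = 14 and a 7-day hold it is 56 − 14 − 7 = 35.

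**5. How far apart the thresholds are**

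Tables 6 and 7 report any treatment-emergent event in 48/60 = 80% of patients and a Grade 3 or 4 event in 22/60 = 37%. These come from other doses and diseases. They show that the two thresholds catch different numbers of patients, and they are not a rate at DL0.

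**The case against.** The strongest reply is that nobody would apply the bullet literally. It stands under a heading about unacceptable events and follows a bullet about dose holds, and 6.3.3.3 already states the DL0 rule in full. Table 3 allows restart with toxicity below Grade 2, so a literal reading could remove a patient at the moment of restart. That suggests shorthand for 6.3.3.3. This is a fair account of the likely intent. But the heading introduces its bullets as the specification of what is unacceptable, and the DL0 bullet supplies no threshold. The investigator-judgment grounds in 7.9.2.5 and 8.2 are separate routes to removal and do not limit it.

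The second reply is that few patients are affected, and this stands. A DL1 patient with inadequate response and low-grade toxicity escalates at the weekly visit, so the hemoglobin route needs a good response at DL1, or a return to DL1 and a further hold. Few toxicity holds fall outside the DLT definition. Conditions present at screening count as adverse events only if they worsen (13.4).

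The day count depends on when benefit is first recorded. From a baseline of 8.5 g/dL the criterion is met at 8.5 + 1.5 = 10.0 g/dL, possibly well before 12. Section 12.6.2 also says that it is still to be completed, so the evaluability consequence is provisional.

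**Conclusion.** The inconsistency is real, and confidence in it is high. Read as written, 7.9.2.3 removes DL0 patients for events at which 6.3.3.3 and Table 3 keep them on treatment. Severity is minor, because the intended meaning is probably the Hold threshold and the affected group is narrow.

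The number of patients cannot be estimated: the documents give neither a rate of step-down to DL0 nor an adverse event rate at 50 mg daily. For a hemoglobin responder stepped down from DL1, 28 to 51 of the 56 days in Table 5 are spent at DL0 if benefit is first recorded at the hold visit, and fewer if it was recorded earlier. For patients who reach DL0 after a DLT the wording does not alter the responder count, because Table 5 already excludes them.

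The finding covers adverse events only. Section 6.3.3.3 also removes a DL0 patient held for hemoglobin above 12 g/dL, which 7.9.2.3 does not list; that difference is not addressed here.

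**What to change.** Replace the DL0 bullet in 7.9.2.3 with: *Adverse events at DL0 that meet the Table 3 toxicity Hold criterion* (">Grade 2 Requiring Change in Treatment"). Leave the bullet on holds longer than 28 days, Section 6.3.3.3 and Table 3 unchanged. The three places then give the same answer in every row of the comparison, using a threshold the protocol already sets. Removal for Hold-level toxicity and investigator discretion are unaffected. If the investigators do intend a stricter rule at the lowest dose, they should state its grade and change 6.3.3.3 and Table 3 to match. The cost is one bullet by amendment, with no extra assessments or patients.
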